7.3 Follow-Up for Drug Discontinuation/Subject Withdrawal from Study

If a patient discontinues study treatment and is withdrawn from the study for any reason, the study site must immediately notify the Sponsor. The date and the reason for study treatment discontinuation / study withdrawal must be recorded on the electronic case report form (eCRF). Patients who withdraw prematurely are to attend an early termination visit, if possible, and complete all assessments.

In the event that a patient discontinues prematurely from the study due to a treatment-emergent adverse event (TEAE) or serious TEAE, the TEAE or serious TEAE will be followed until it resolves (returns to normal or baseline values) or stabilizes, or until it is judged by the Investigator to be no longer clinically significant.

Once a patient is withdrawn from the study, the patient may not re-enter the study.

8 Treatments

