9.2 Procedures by Study Period

Assessments and study procedures are to be performed as outlined in The Schedule of Assessments, Table 9-1. The PK, ADA, Biomarker, and Glycan Sampling Schedule is provided in Table 9-2 (Part A – Dose Escalation) and Table 9-3 (Part B - Expansion).

The Investigator may at his/her discretion arrange for a patient to have an unscheduled assessment, especially in the case of AEs that require follow-up or an AE considered by the Investigator to be possibly related to the use of study drug. The unscheduled visit page on the eCRF must be completed. Additional visits to follow-up positive ADA may happen after end of study (Table 9-1).

Table 9-1Schedule of Assessments

| Study Procedure | Screening Visit** | Treatment Period | | | | | | |
|--|-------------------|------------------|---|--------|---|---|---------|--|
| Cycle (C) # | - | Cycle 1 | | | | Cycle 2-13 | | |
| Cycle # and Day | | C1D1 | 1D1 C1D8 C1D15 C1D22 | | C1D22 | | | |
| Window period (days) | -28 to -1 days | -1* | ±1 | ±3 | ±3 | ± 3 days | ±7 days | |
| Informed consent ^a | Х | | | | | | | |
| Demographics | Х | | | | | | | |
| Eligibility screening | Х | Х | | | | | | |
| Medical history ^b | X | Х | | | | | | |
| Physical examination ^c | Х | Х | Х | Х | Х | D1 of each Cycle | X | |
| Height, weight ^d | Х | X X X X | | | | D1 of each Cycle | X | |
| Vital signs ^e | X | X X X X | | | Х | D1, D8, D15, D22 of each Cycle | Х | |
| ECOG ^f | Х | | | | | D1 of each Cycle | Х | |
| 12-lead ECG ^g | Х | Х | | | | | | |
| Pregnancy testing ^h | Х | | | | | | X | |
| Tumor biopsy ⁱ | X** | | | | | | | |
| Hematology and Biochemistry ^j | Х | Х | | | | D1 of each Cycle | Х | |
| Coagulation and Urinalysis ^k | Х | Х | | | | | | |
| Drug administration ¹ | | Х | Х | Х | Х | D1, D8, D15, D22 of each 28 day cycle | | |
| Pharmacokinetic sample ^m | | | | See fo | otnote m | and Table 9-2 (Part A) and Table 9-3 (Part B) | | |
| Immunogenicity (ADA) ⁿ | | | | See fo | otnote n | and Table 9-2 (Part A) and Table 9-3 (Part B) | | |
| Biomarkers ^o | Х | | | See fo | otnote o | and Table 9-2 (Part A) and Table 9-3 (Part B) | | |
| Radiology evaluations (CT or MRI) ^p | X | | Q8wk (±1 wk) for the first then Q12wk (±1 wk) th | | Q8wk (±1 wk) for the first 6 months, then Q12wk (±1 wk) thereafter | X | | |
| Concomitant medications | • | • | • | • | • | | | |
| Adverse events | | | | | | | | |

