EOS/ET - End of Study/Early Termination. EoS Visit is the safety follow-up visit, conducted 28±7 days after the last OBI-888 dose. ET visit lab assessments will be conducted for subjects discontinuing study treatment, if last available tests are before 2 weeks.

*The -1 day window (1 day prior) for C1D1 is for safety laboratory assessments. Blood can be drawn 1 day prior to initiation of study drug infusion on C1D1. Safety laboratory results should be available and reviewed by the Investigator prior to the OBI-888 administration.

** All patients are required to provide a tumor biopsy sample, unstained slides (preferred) or a formalin fixed paraffin embedded (FFPE) tissue block at the initiation of screening visit for screening of Globo H overexpression and confirmation for eligibility of subjects for Part B. Patients with a confirmed and documented Globo H H-score of ≥ 100 are eligible for the study, and will subsequently enter the 28-day screening period to complete the remaining screening procedures.

Footnotes:

- a. Informed consent to be obtained before any other study procedures are performed.
- b. Medical history to include previous cancer therapies, cancer history, and past and ongoing concomitant illnesses.
- c. A complete physical examination is required at screening and at discontinuation. Directed physical examinations may be limited to problem focused review of symptoms and major organ systems at D1 of each cycle and prior to infusion.
- d. Height to be obtained at screening only. Weight obtained at D1 of each cycle, prior to infusion. If during treatment a patient's body weight changes by >10% from the baseline value, the OBI-888 dose should be adjusted.
- e. Vital signs include temperature, blood pressure and pulse (at supine position) prior to every infusion. Temperature measurement will be obtained as clinically indicated.
- f. ECOG performance status: at baseline, C2D1 and end of study/early termination.
- g. 12-lead ECG: at screening and pre and post infusion at C1D1 (within one hour after end of infusion).
- h. Pregnancy testing should be performed in females of childbearing potential only. A urine or serum pregnancy test is acceptable.

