- i. Tumor biopsy samples are mandatory at screening visit. Fresh (preferred) tissue or archival tissue is acceptable. A minimum of 3 slides are required for the central laboratory Globo H assay for determination of eligibility. Up to 12 unstained additional slides should be provided, depending upon availability, for the protocol-defined exploratory studies.
- j. Hematology and Serum chemistry (Laboratory Assessments: Table 12-1). Blood draw is prior to OBI-888 infusion.

Hematology: hematocrit, hemoglobin, red blood cell (RBC) count, white blood count (WBC), absolute counts of leukocytes, neutrophils, lymphocytes, monocytes, eosinophils, basophils, and platelet count.

Serum chemistry: sodium, potassium, chloride, bicarbonate, BUN, creatinine, glucose, calcium, phosphorus, magnesium, total protein, albumin, ALT, AST, ALP, creatine kinase, LDH, total bilirubin, and uric acid. Creatinine clearance will be calculated by Cockcroft Gault equation at the screening visit, Week 1 and EOS/early termination.

k. Coagulation, and Urinalysis (Laboratory Assessments: Table 12-1). Blood draw and urine collection is prior to OBI-888 infusion. Coagulation: PT, aPPT, and INR.

Urinalysis: specific gravity, pH, protein, glucose, ketones, bilirubin, urobilinogen, blood, nitrite, leukocyte esterase as assessed by dipstick. A microscopic urinalysis (only if needed) evaluating white blood cells, red blood cells, epithelial cells, bacteria, cast and crystals

- OBI-888 is given in cycles with each individual cycle consisting of 28 days (4-week cycle). IP is administered on a weekly basis (within cycle as C1D1, C1D8, C1D15, and C1D22; C2D1, C2D8, and so on; until progressive disease, unacceptable toxicity, or decision by the Investigator or patient to discontinue treatment.
- m. Pharmacokinetic: (for analysis of serum concentration of OBI-888). Detailed schedules are provided in Table 9-2 (Part A) and Table 9-3 (Part B).
- n. Immunogenicity studies (ADA): ADA samples will be collected at the same time points, along with pre-infusion only PK samples. No post-infusion ADA samples will be collected. Detailed schedules are provided in Table 9-2 (Part A) and Table 9-3 (Part B). For subjects with persistent antibodies at end of study, an additional ADA sample will be collected at 4 months after the end of study visit.
- o. Biomarker: Detailed schedules are provided in Table 9-2 (Part A) and Table 9-3 (Part B).

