10. ANALYTICAL PLAN AND STATISTICAL METHODS

10.1 GENERAL CONVENTIONS AND STATISTICAL CONSIDERATIONS

All statistical analyses will be conducted and data appendices will be created using the SAS system version 9.4 or higher.

Data collected in this study will be presented in patient data listings and summary tables.

Descriptive statistics (number of patients with non-missing values, mean, standard deviation, median, minimum, and maximum) will be presented for continuous variables. All raw data will be presented to the original number of decimal places. Means and medians will be presented to 1 more decimal place than in the raw data. Standard deviations will be presented to 2 more decimal places than in the raw data.

Frequency distributions (counts and percentages) will be presented for categorical variables. Discrete variables that are ordinal-scaled (e.g., ECOG performance score) will additionally be presented with mean scores and standard deviations. If not specified otherwise, the number of observations with non-missing values will be the denominator for percentage calculation. Further details on the handling of missing observations are presented in section 10.3.

If days are converted to months, a factor of 30.4 days/month will be used. If days are converted to years, a factor of 365.25 days/year will be used. Time will be shown in study weeks, i.e. number of weeks from the first administration of any study drug.

Dose escalation (Part A). The dose-escalation analysis will be presented by OBI-888 dose (5 mg/kg, 10 mg/kg or 20 mg/kg) cohorts and overall. The following cohorts and overall will be presented:

- OBI-888 5 mg/kg
- OBI-888 10 mg/kg
- OBI-888 20 mg/kg
- Dose Escalation Total

Expansion cohorts (Part B). The expansion part analysis will be presented by cancer diagnosis. The following cohorts and overall will be presented:

- Cohort 1: Pancreatic cancer
- Cohort 2: Esophageal cancer
- Cohort 3: Gastric cancer
- Cohort 4: Colorectal cancer
- Cohort 5: Basket (any solid tumor type other than those included in Cohorts 1 through 4)

Review Status: Final Version: 2.0 Version Date: 02JUN2022

Cohort Expansion Total

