10.8.2 LABORATORY DATA

Tables by visit and by NCI CTC grades (grade 0, grade 1, grade 2, grade 3, grade 4, grade 5) will be presented by laboratory test, where applicable. Worst-post baseline NCI CTC grade for applicable laboratory tests will be also summarized.

Urinalysis results (normal/ abnormal – low/ abnormal - high) will be summarized by visit.

Data listings will be produced for all collected laboratory data, including pregnancy test results.

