14. APPENDIX I. SCHEDULE OF ASSESSMENTS

TABLE 14-1 SCHEDULE OF ASSESSMENTS

Schedule of Assessments

Study Procedure	Screenin g Visit**		Treatment Period						
Cycle (C) #	-	Cycle 1				Cycle 2-13			
Cycle # and Day		C1D 1	C1D 8	C1D C1D1 C1D 8 5 22					
Window period (days)	-28 to -1 days	-1*	±1	±3	±3	±3 days	±7 days		
Informed consent ^a	Χ								
Demographics	Χ								
Eligibility screening	Χ	Χ							
Medical history ^b	Χ	Χ							
Physical examination ^c	Х	Х	Χ	Х	Х	Х	Х		
Height, weight ^d	Χ	Χ	Χ	Χ	Χ	Χ	Х		
Vital signs ^e	Χ	Х	Χ	Χ	Χ	X	Х		
ECOG ^f	Χ					C2D1 only	Х		
12-lead ECG ⁹	Χ	Χ	Χ			C2D1 only	Χ		
Pregnancy testing ^h	Χ						Χ		
Tumor biopsyi	X**								
Hematology and Biochemistry ^j	Х	Х	Х	Х	Х	Every 2 weeks (D1 and D15 of each Cycle)	Х		
Coagulation and Urinalysis ^k	Х	Х				Every 2 cycles, D1 (C2 C4, C6, C8, C10, C12)	Х		
Drug administration ^l		Х	Χ	Х	Χ	D1, D8, D15, D22 of each 28 day cycle			
Pharmacokinetic sample ^m		See	footn	ote m	and 7	Table 14-2 (Part A) and Table (Part B)	e 14-3		
Immunogenicity (ADA) ⁿ		See	footr	ote n	and T	able 14-2 (Part A) and Table (Part B)	14-3		
Biomarkers ^o	Х	See	footr	ote o	and T	able 14-2 (Part A) and Table (Part B)	: 14-3		
Radiology evaluations (CT or MRI) ^p	Х		End of every 2 cycles			х			
Concomitant medications	Х	Х	Х	Х	Х	X	Х		
Adverse events		Х	Χ	Χ	Χ	X	Χ		

EOS/ET - End of Study/Early Termination. EoS Visit is the safety follow-up visit, conducted

Review Status: Final Version: 2.0

Version Date: 02JUN2022

28±7 days after the last OBI-888 dose. ET visit lab assessments will be conducted for patients discontinuing study treatment, if last available tests are before 2 weeks.

*The - 1 day window (1 day prior) for C1D1 is for safety laboratory assessments. Blood can be drawn 1 day prior to initiation of study drug infusion on C1D1. Safety laboratory results should be available and reviewed by the Investigator prior to the OBI-888 administration.

** All patients are required to provide a tumor biopsy sample, unstained slides (preferred) or a FFPE tissue block at the initiation of screening visit for screening of Globo H overexpression and confirmation for eligibility of patients for Part B. Patients with a confirmed and documented Globo H H-score of ≥ 100 are eligible for the study, and will subsequently enter the 28-day screening period to complete the remaining screening procedures.

Footnotes:

- a. Informed consent to be obtained before any other study procedures are performed.

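### In about the first two weeks of treatment, the pre-dose baseline sample can excuse a patient from early-termination labs, leaving no scheduled post-dose value if the 28-day follow-up visit is also missed

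*Protocol*

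**What the plan says.** - **Waiver.** The note under protocol Table 9-1 (Section 9.2) reads: "ET visit lab assessments will be conducted for subjects discontinuing study treatment, if last available tests are before 2 weeks". The same note stands under SAP Table 14-1.
- **Section 7.3.** "Patients who withdraw prematurely are to attend an early termination visit, if possible, and complete all assessments". No laboratory waiver is mentioned there.
- **Sampling in protocol Table 9-1.** Hematology and biochemistry are marked at screening, at C1D1, from Cycle 2 at "D1 of each Cycle", and in the combined EOS/ET column. C1D8, C1D15 and C1D22 are blank. Footnote j adds "Blood draw is prior to OBI-888 infusion", and the C1D1 window note says "Blood can be drawn 1 day prior to initiation of study drug infusion on C1D1".
- **End of study (EoS).** The sentence just before the waiver defines EoS as a safety follow-up visit 28±7 days after the last dose. Section 6.1.3 also provides for it. The waiver sentence names only the ET visit, but the table has one column for both.
- **Analysis.** SAP 10.2 counts a value dated on the first-dose day as baseline. SAP 10.8.2 states: "Worst-post baseline NCI CTC grade for applicable laboratory tests will be also summarized". Under SAP 10.1, unless something else is specified, "the number of observations with non-missing values will be the denominator for percentage calculation".
- **SAP schedule.** SAP Table 14-1 marks these labs weekly in Cycle 1 and then "Every 2 weeks (D1 and D15 of each Cycle", although SAP Section 3 says that the SAP covers protocol version 5.0.

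**The concern.** A waiver based only on the age of the last test works when samples are frequent enough that a recent one reflects recent dosing. In protocol Table 9-1 they are four weeks apart and always taken before the infusion. In Cycle 1, a test less than two weeks old is the baseline itself. It says nothing about the effect of the drug, yet it can excuse the patient from the one laboratory sample due on leaving treatment.

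CTCAE-graded laboratory abnormalities are a primary endpoint (protocol 5.2.1, SAP 8.1). The abbreviated report concentrates on safety and exposure. SAP Section 11 drops the shift tables and other laboratory summaries, so the tables in SAP 10.8.2 carry this endpoint. A treated patient with no post-dose value would not appear in the worst-grade table. The two protocol instructions also differ, so a site can omit the ET sample and still be following one of them.

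**Working it through.** The plan states no figure to reproduce. The check is a count of days.

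**Inputs.** Nominal visit days, with C1D1 = Day 1. Protocol Table 9-1 draws fall on Days 1, 29, 57 and so on. SAP Table 14-1 draws fall on Days 1, 8, 15, 22, 29, 43 and so on. EoS is at last dose + 21 to + 35 days. Infusions are on Days 1, 8, 15 and 22.

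**Rule.** Age of last test = ET day − day of last draw. ET labs are waived if the age is 14 days or less. The note does not say whether the two weeks run back from the ET visit or from the decision to stop; the ET visit is assumed here.

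**Step 1: Cycle 1, protocol Table 9-1.**
- Draw on Day 1: waived if ET day − 1 ≤ 14, that is Days 2-15.
- Draw the day before (counted as day 0): waived if ET day ≤ 14, that is Days 2-14.
- If a test exactly 14 days old does not excuse, each range ends one day earlier.
- On all these days the only earlier scheduled value is baseline under SAP 10.2. One or two infusions have followed it on the nominal schedule, or three if the Day 15 infusion is given before an ET visit that day.
- On Days 16-28 with a Day 1 draw, the age is 15-27 days, so ET labs are required.

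**Step 2: Cycle 2 onward.** The Day 29 sample is post-baseline, so the patient is in the worst-grade table whatever happens at ET. The waiver can then only miss an abnormality that arises after the latest Day 1 draw.

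**Step 3: SAP Table 14-1.** With a Day 8 draw, the interval with no post-baseline value shrinks to about Days 2-7, or to Day 8 or 9 if the Day 8 sample is still outstanding at the ET visit.

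**Step 4: what EoS recovers.**
- Last dose on Day 1: EoS on Days 1 + 21 = 22 to 1 + 35 = 36.
- Last dose on Day 8: EoS on Days 29-43.

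A patient who attends has a post-baseline value, but the first scheduled one comes 21-35 days after the last dose.

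**Step 5: effect on a percentage, by assumption.** Take the first-stage cohort of 9, with one event among the patients who have values and m = 1, 2 or 3 patients without a post-baseline value.

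| m | Shown, 1/(9 − m) | True if none of the m had the event, 1/9 | True if all had it, (1 + m)/9 |
|---|---|---|---|
| 1 | 12.5% | 11.1% | 22.2% |
| 2 | 14.3% | 11.1% | 33.3% |
| 3 | 16.7% | 11.1% | 44.4% |

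With 30 patients, the table would show 3.4% to 3.7%, against 3.3% if none of the missing had the event and up to 4/30 = 13.3% if all three did. If the only event is in the one missing patient of 9, the table shows 0/8 instead of 1/9. The documents do not give m, so these figures show only how sensitive the table is.

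**The case against.** The strongest reply is that the EoS visit closes the gap. It is a separate visit, its column is marked for these labs, and the waiver does not mention it. A reader might infer from the waiver alone that anyone leaving in the first two weeks drops out of the table. The documents do not support that: EoS must also be missed, or the site must treat ET as taking its place, which the combined column leaves open. This objection stands as a limit on reach.

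The two rules can also be read together. The note speaks of stopping treatment, after which EoS still follows; Section 7.3 speaks of withdrawing early, for which everything is done at ET. That reading is possible, but neither place says so, and both concern the same ET visit.

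A reader might further infer that the loss is informative because early leavers include those stopping for toxicity. That is plausible but not shown. A patient stopped for a laboratory toxicity has already had the test that revealed it. Unscheduled assessments are allowed (Section 9.2), and clinically significant results are recorded as adverse events and followed (Section 12.4). What remains exposed is the abnormality that causes no symptoms and prompts no test.

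The denominator is a default that applies only where nothing else is specified. The table shells are in a separate document, so the worst-grade denominator cannot be confirmed. That caveat also stands.

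**Conclusion.** The concern holds in a limited form and should be corrected. Under protocol Table 9-1, an ET visit on about Cycle 1 Days 2-15 (Days 2-14 if baseline was drawn the day before) can pass without labs on the strength of a pre-dose sample, and Section 7.3 says otherwise. Loss from the worst-grade table additionally requires that EoS is missed or replaced, that no unscheduled test was done, and that the default denominator applies.

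Two larger readings should be avoided. The waiver covers about 14 of the 28 days of a cycle, from which a reader might infer that half of early leavers are affected. It is a share of calendar days; the documents give no distribution of stopping times, and from Cycle 2 on nobody leaves the table for this reason. Nor does the reported 30-hour half-life show that an abnormality would have resolved by EoS, because drug elimination does not measure laboratory recovery.

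By March 2020, 14 Part A and 3 Part B patients had been enrolled. Version 5.0 is dated May 2020, so the gap mainly concerns Part B patients treated under that version.

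**What to change.** 1. Reconcile the note under protocol Table 9-1, and its copy under SAP Table 14-1, with Section 7.3, so that ET hematology and chemistry are not waived on the basis of a sample taken before the last OBI-888 infusion. If a waiver is kept for recent samples taken after that infusion, Section 7.3 should mention it.
2. State whether an ET visit replaces the EoS visit or comes in addition to it.
3. Align the laboratory schedule in SAP Table 14-1 with Table 9-1 of protocol version 5.0, which the SAP says it covers.

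The cost is a few sentences in the two documents, and one routine blood draw, at a visit already marked for these labs, for each patient who would have been waived.
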